5.8.1 Treatment after Initial Radiologic Progression (irRECIST-based Management)

Note: irRECIST-based management is ONLY applicable in cases where metastatic RCC was identified pre-operatively and the subject is receiving post-resection MK-3475.

Immunotherapeutic agents such as pembrolizumab may produce antitumor effects by potentiating endogenous cancer-specific immune responses. The response patterns seen with such an approach may extend beyond the typical time course of responses seen with cytotoxic agents, and can manifest as a clinical response after an initial apparent increase in tumor burden (i.e., pseudoprogression) or even the appearance of new lesions. Standard RECIST-based assessment of disease progression may, thus, not provide an accurate assessment of response to immunotherapeutic agents such as pembrolizumab. For this reason, irRECIST has been developed to help guide treatment decisions during tumor immunotherapy.

For subjects who have initial radiological evidence of radiological PD by RECIST 1.1 as determined by the site, the investigator may elect to continue a subject on study treatment until repeat imaging is obtained (irRECIST-based management) (see [Table 9](#)). This clinical judgment decision by the investigator should only be made if the subject is clinically stable, based on clinical factors including performance status, clinical symptoms, and laboratory data. Such subjects may continue to receive study treatment and a imaging-based tumor assessment should be repeated ≥ 4 weeks later in order to reassess PD per investigator assessment.

Clinical stability is defined by the following:

- Absence of signs and symptoms of clinically significant progression of disease, including worsening of laboratory values,
- No decline in ECOG performance status,
- Absence of rapid progression of disease, AND
- Absence of tumor progression at critical anatomical sites that requires urgent alternative medical intervention (e.g., CNS metastasis with potential for cord compression)

NOTE: Subjects exhibiting toxicity from trial therapy as outlined in Section 5.2.1.2 and 7.2 may NOT continue to receive trial therapy.

NOTE: Any subject deemed **clinically unstable** should be discontinued from trial treatment at investigator-assessed 1st radiologic evidence of PD and is not required to have repeat imaging for PD confirmation.

In determining whether or not the tumor burden has increased or decreased per irRECIST, the investigator should consider all target and non-target lesions as well as any incremental new lesion(s).

Upon repeat imaging, PD will be confirmed if ANY of the following occur by irRECIST:

- Tumor burden remains $\geq 20\%$ and at least 5 mm absolute increase compared to nadir
- Non-target disease resulting in initial diagnosis of PD is worse (qualitative assessment)
- New lesion resulting in initial diagnosis of PD is worse (qualitative assessment)
- Additional new lesion(s) since last evaluation
- Additional new non-target lesion progression since last evaluation

If repeat imaging confirms PD due to any of the scenarios listed above, subjects will be discontinued from trial therapy (exception noted below in this Section 5.8.1).

Upon repeat imaging, PD will have failed to be confirmed if ALL of the following occur by irRECIST:

- Tumor burden is $< 20\%$ or < 5 mm absolute increase compared to nadir
- Non-target disease resulting in initial diagnosis of PD is stable or improved (qualitative assessment)
- New lesion resulting in initial diagnosis of PD is stable or improved (qualitative assessment)
- No incremental new lesion(s) since last evaluation
- No incremental new non-target progression since last evaluation

If repeat local site imaging fails to confirm PD by irRECIST and the subject continues to be clinically stable, treatment may continue and follow the regular imaging schedule.

When feasible, subjects should not be discontinued until after PD is confirmed by the local site investigator radiology assessment. This allowance to continue treatment despite initial radiologic PD takes into account the observation that some subjects can have a transient tumor flare in the first few months after the start of immunotherapy, and then experience subsequent disease response. Subjects who are deemed clinically unstable are not required to have repeat tumor imaging for confirmation of PD. Tumor flares include any of the following scenarios:

- Worsening of existing target lesion(s)
- Worsening of existing non-target lesion(s)
- Development of new lesion(s)

Additional details about irRECIST are referenced in the Merck TIP Sheet for RECIST 1.1 and irRECIST.

Table 9 Imaging and Treatment after First Radiologic Evidence of PD (irRESIST-based Management) (Post-Resection MK-3475 Only)

| | Clinically Stable | | Clinically Unstable | |
|---|--|---|--|--|
| | Imaging | Treatment | Imaging | Treatment |
| 1st radiologic evidence of PD by RECIST 1.1 | Repeat imaging at \geq 4 weeks at site to confirm PD | May continue study treatment at the local site investigator's discretion while awaiting confirmatory tumor imaging by site by irRECIST. | Repeat imaging at \geq 4 weeks to confirm PD per physician discretion only | Discontinue treatment |
| Repeat tumor imaging confirms PD by irRECIST at the local site | No additional imaging required | Discontinue treatment (exception is possible upon consultation with Sponsor) | No additional imaging required | N/A |
| Repeat tumor imaging shows SD, PR or CR by irRECIST at the local site | Continue regularly scheduled imaging assessments | Continue study treatment at the local site investigator's discretion | Continue regularly scheduled imaging assessments | May restart study treatment if condition has improved and/or clinically stable per investigator's discretion. Next tumor image should occur according to the regular imaging schedule outlined in the protocol |

5.9 Subject Replacement Strategy

If a subject discontinues from the trial, a replacement subject may be enrolled if deemed appropriate by the investigator and Sponsor. The replacement subject will generally receive the same treatment or treatment sequence (as appropriate) as the subject being replaced. The replacement subject will be assigned a unique randomization number. The trial site should contact the Sponsor for the replacement subject's randomization number.

5.10 Beginning and End of the Trial

The overall trial begins when the first subject signs the informed consent form. The overall trial ends when the last subject completes the last study-related phone-call or visit, discontinues from the trial or is lost to follow-up (i.e. the subject is unable to be contacted by the investigator).

A trial may be paused during review of newly available preclinical/clinical safety, pharmacokinetic, pharmacodynamic, efficacy or biologic data or other items of interest, prior to a final decision on continuation or termination of the trial. It may be necessary to keep the trial open for gathering/reviewing of additional supportive data to optimally complete the objective(s) of the trial. If necessary, the appropriate amendment(s) to the protocol and/or appropriate communication(s) will be generated. The overall trial end will then not be identified until the Sponsor has made the decision to end the trial following this review period. The Competent Authority(ies) and Institutional Review Board(s)/Independent Ethics Committee(s) [IRB(s)/IEC(s)] will be appraised of the maximum duration of the trial beyond the last subject out and the justification for keeping the trial open.

5.11 Clinical Criteria for Early Trial Termination

There are no pre-specified criteria for terminating the trial early.

6.0 TRIAL FLOW CHART

6.1 Trial Flow Chart - Patients Randomized to Neoadjuvant MK-3475

| Trial Period: | Screening | Randomization ^a | Pretreatment Core Biopsy | MK-3475 | | SOC Tumor Resection | Post-operative Follow Up |
|--|----------------|----------------------------|--------------------------|---------|----|---------------------|--------------------------|
| Week: | -2 | -2 | -1 | 1 | 4 | 7 | 12 ^b |
| Scheduling window (days) | ±14 | ±14 | ±6 | ±3 | ±3 | -7/+14 | -5/+7 |
| Administrative Procedures | | | | | | | |
| Informed Consent ^c | X | | | | | | |
| Informed Consent for Future Biomedical Research ^d | X | | | | | | |
| Inclusion/Exclusion Criteria | X | | | | | | |
| Subject Identification Card | X | | | | | | |
| Medical History | X | | | | | | |
| ECOG Performance Scale Assessment | X | | | | | | |
| Concomitant Medication Review ^e | X | | X | X | X | X | X |
| Clinic Procedures/Assessments | | | | | | | |
| Full Physical Examination ^f | X | | | X | X | | |
| Directed Physical Examination ^f | | | | | | X ^g | X |
| Vital Signs, Weight and Height ^h | X | | | X | X | X ^g | X |
| 12-Lead Electrocardiogram (performed locally) | X ⁱ | | as clinically indicated | | | | |
| Tumor Core Needle Biopsy ^j | | | X ^k | | | X ^l | |
| MK-3475 Administration ^m | | | | X | X | | |
| SOC Tumor Resection | | | | | | X | |
| Adverse Events Monitoring ⁿ | X | | X | X | X | X | X |
| Assessment of Surgical Complications | | | | | | | X ^o |
| Laboratory Procedures/Assessments | | | | | | | |
| Pregnancy Test- Urine or Serum β-HCG or FSH ^p | X ⁱ | | | X | | | |
| PT/INR and aPTT | X ⁱ | | | | | X ^{q,r} | X |
| CBC with Differential | X ⁱ | | | X | X | X ^q | X |
| Chemistry | X ⁱ | | | X | X | X ^q | X |
| Urinalysis | X ⁱ | | | | | | |
| T3, FT4, and TSH | X ⁱ | | | | X | | X |
| Blood for HLA typing | | | X ^{s,t} | | | | |
| HIV/Hepatitis Screen | X ⁱ | | | | | | |

| Trial Period: | | Screening | Randomization^a | Pretreatment Core Biopsy | MK-3475 | | SOC Tumor Resection | Post-operative Follow Up |
|--|--|------------------|----------------------------------|---------------------------------|----------------|----------------|----------------------------|---------------------------------|
| Week: | | -2 | -2 | -1 | 1 | 4 | 7 | 12 ^b |
| Scheduling window (days) | | ±14 | ±14 | ±6 | ±3 | ±3 | -7/+14 | -5/+7 |
| Protocol-Specific Specimen Collection | | | | | | | | |
| Tissue Collection | Fresh tumor tissue for shipping (TIL analysis, histoculture, tumor cell isolation and IMR expression analysis) | | | | | | X | |
| | Tumor tissue for FFPE (IHC; DNA for mutational analysis, TCR utilization, promoter methylation analysis; RNA for gene expression and miRNA analysis) | | | X ^u | | | X ^{v,w} | |
| | Fresh tumor tissue for snap freezing (DNA isolation, metabolic profiling, laser capture microdissection) | | | | | | X | |
| | Fresh non-malignant kidney tissue from resected tumor specimen for snap freezing (DNA isolation) | | | | | | X | |
| | Fresh tumor tissue in RNAlater solution (RNA extraction, gene expression) | | | | | | X | |
| | Fresh non-malignant kidney tissue in RNAlater solution (RNA extraction, gene expression) | | | | | | X | |
| Blood | PBMC Phenotypic Analysis | | | X ^t | | | X ^q | X |
| | PBMC Isolation and Cryopreservation (Antigen-specific T cell response evaluation) | | | X ^t | | | X ^q | X |
| | Plasma (miRNA, and exosome evaluation) | | | X ^t | | | X ^q | X |
| | Serum (biomarkers) | | | X ^t | | | X ^q | X |
| | Serum (PK/PD) | | | | X ^x | X ^y | X ^q | X |
| | RNA isolation (gene expression, miRNA expression) | | | X ^t | | | X ^q | X |
| | DNA isolation (TCR utilization) ^z | | | X ^t | | | X ^q | X |
| | B cell isolation and transformation | | | | | | | |
| Urine for exosome isolation and analysis | | | | X ^t | | | X ^{aa} | X |

- a. Randomization, initially 2:1 neoadjuvant MK-3475:controls. Randomization will occur only after written consent is obtained and will occur after all screening assessments have been completed. Randomization can occur at any time point after screening and prior to core biopsy.
- b. This follow up visit must occur no less than 30 days after the day of SOC tumor resection.
- c. Written consent must be obtained prior to performing any protocol-specific procedure. Results of a test performed prior to the subject signing consent as part of routine clinical management are acceptable in lieu of a screening test if performed within 28 days prior to screening.
- d. If the subject signs the FBR consent, leftover samples may be kept for Future Biomedical Research.
- e. Prior medications – Record all medications taken within 28 days of screening visit. Concomitant medications – Enter new medications started during the trial through 30 days after the last dose of trial treatment. Record all medications taken for SAEs as defined in Section 7.2
- f. Full PE at screening and neoadjuvant MK-3475 treatment visits; Directed PE for all other visits.
- g. These procedures may be performed up to 36 hours prior to the start of the SOC RCC tumor resection surgical procedure.
- h. Vital signs include temperature, pulse, respiratory rate, weight and blood pressure. Height will be measured at screening visit only. Vital signs will be collected at screening, prior to the administration of each dose of trial treatment, at SOC tumor resection, and at post-operative follow-up.
- i. Laboratory tests for screening are to be performed within 28 days prior to the first dose of trial treatment. See section 7.1.3 for details regarding laboratory testing.
- j. If a diagnostic biopsy has already been performed per local SOC and sufficient tissue from that sample is available and will be submitted for all study-related analyses specified for the preoperative biopsy tissue, the study-specified pretreatment biopsy will not be required and these assessments should be performed on the day that pretreatment blood and urine samples (see footnote t below) are collected.
- k. Percutaneous core needle biopsy of RCC performed under image guidance. This procedure may take place any time between randomization to the MK-3475 treatment group and the start of treatment with MK-3475. This study-prescribed pretreatment core needle biopsy is not required if a diagnostic biopsy has been performed per local SOC for diagnostic purposes, this biopsy will have been performed within 45 days prior to the first dose of MK-3475, and sufficient tissue is available from such a specimen for all study-related analyses specified for the pretreatment biopsy.
- l. During the surgical procedure and prior to cross-clamping of the renal artery, under direct vision a core needle biopsy of the RCC may be performed at the discretion of the operating surgeon and subject to local IRB approval.
- m. The number of doses of MK-3475 may be increased to three doses, based on the results of the first interim analysis, as described in Section 8.0 (See [Table 12](#) for the flow chart should this occur).
- n. AEs and laboratory safety measurements will be graded per NCI CTCAE version 4.0. All AEs, whether gradable by CTCAE or not, will also be evaluated for seriousness.
- o. At this visit, the occurrence of any surgical complications within 30 days of the operative procedure will specifically be assessed.
- p. For female subjects of reproductive potential, a urine pregnancy test should be performed within 72 hours of the first dose of trial treatment. If urine pregnancy results cannot be confirmed as negative, a serum pregnancy test performed by the local study site laboratory will be required. Pregnancy tests (serum and/or urine tests) should be repeated if required by local guidelines. For women thought to be post-menopausal, serum FSH will be measured to confirm post-menopausal status.
- q. Blood for study related analyses may be collected at any time prior to surgery on the day of surgery. Ideally these blood samples will be collected via the iv cannula placed in preparation for surgery, but these samples may also be collected via venipuncture earlier on the day of surgery, at the discretion of the clinical care team
- r. Blood for assessment of these coagulation parameters may be drawn up to 72 hours before the day of SOC tumor resection, at the discretion of the operative team. If such a sample is collected, a sample for these tests will not need to be collected on the day of surgery.
- s. Low resolution HLA-A and B typing, to be performed by local HLA typing laboratory.
- t. Blood and urine samples should be collected on the day of the pretreatment core biopsy. However, if tissue from a biopsy previously performed per local SOC for diagnostic purposes will be submitted for all specified study-related analyses, these blood and urine samples should be collected as close to the time of this biopsy as possible and must be collected prior to the first dose of MK-3475.

- u. A minimum of 3 18-gauge core biopsy tumor samples will be collected. The harvested cores will be placed in single cassette for formalin fixation and paraffin embedding. The entire specimen will then be cut onto slides. After the diagnosis of RCC is confirmed by the local site pathologist, the remaining tissue sections will be used for study related analyses.
- v. A minimum of 3 18-gauge core biopsy tumor samples may be collected intraoperatively under direct vision by the surgeon prior to cross-clamping of the renal artery on the side of the RCC. The harvested cores will be placed in single cassette for formalin fixation and paraffin embedding. The FFPE block will then be shipped to Central Laboratory.
- w. Following tumor resection, additional tumor tissue will be collected for formalin fixation and paraffin embedding. These FFPE blocks will then be shipped to Central Laboratory.
- x. Blood sample to be collected 30 minutes after the completion of MK-3475 dosing.
- y. Blood samples to be collected immediately prior to and 30 minutes after the completion of MK-3475 dosing.
- z. Any leftover extracted DNA will be stored for future biomedical research if the subject signs the FBR consent.
- aa. Urine will be collected prior to surgery on the day of the surgical RCC resection.

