4.2.3.3 Planned Exploratory Biomarker Research

Biomarker research to identify factors important for MK-3475 treatment responses will be pursued. Tissues to be collected and assays to be performed include but are not limited to the following:

Gene expression profiling

RNA extracted from FFPE core biopsy tissue, FFPE resected RCC specimens, fresh resected RCC tissue in RNAlater solution, and whole blood will be utilized for gene profiling. Pretreatment gene expression profiles may predict which RCC tumors are infiltrated by immune cells in response to MK-3475 therapy. By comparing profiles in tumor tissues and whole blood collected before and after neoadjuvant MK-3475, changes in gene expression induced during MK-3475 treatment will be identified and will be used to more fully understand the mechanism of action of MK-3475.

Blood collection for genomic, genetic, and proteomic analysis

Blood will be collected at the time of biopsy (baseline), at the time of surgical tumor resection, and one month postoperatively. Blood collected in Paxgene tubes will also be used for DNA extraction and subsequent sequencing-based TCR utilization analysis (for correlation with intratumoral TCR utilization). Additional blood collected in Paxgene tubes will be used for RNA extraction and subsequent gene profiling for comparison to and correlation with tumor gene profiles. Whole blood samples will be analyzed by flow

cytometry to determine the phenotype of PBMC, and for subject that are HLA-A2+, pentamer staining will be performed (see below). PBMC will also be isolated from whole blood and then cryopreserved for later functional analysis.

Plasma and serum will also be collected and frozen for later analysis. Assays to be performed using plasma or serum may include but will not be limited to measurement of sPD-L1 levels using an ELISA assay recently developed at Merck, protein profiling, miRNA profiling, exosome isolation and analysis, assessment of serum antibodies, and circulating tumor DNA analysis. A recent study suggested that miRNAs 21 and 378 levels in plasma were predictive of response in patients with metastatic RCC treated with everolimus [78].

Determining the influence of tumor tissue source (FFPE vs frozen tissues) on DNA-based methods for quantitating RCC T cell infiltration

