5.1.3 Subject Exclusion Criteria

The subject must be excluded from participating in the trial if the subject:

1. Is currently participating and receiving study therapy or has participated in a study of an investigational agent and received study therapy or used an investigational device within 4 weeks of screening.
2. Has a diagnosis of immunosuppression or has received systemic steroid therapy or any other form of immunosuppressive therapy within 4 weeks prior to screening.
3. Has had prior chemotherapy, targeted small molecule therapy, or radiation therapy for the treatment of RCC.
4. Has a known additional malignancy (other than RCC) that is progressing or requires active treatment. Exceptions include basal cell carcinoma of the skin, squamous cell carcinoma of the skin, and *in situ* cervical cancer that has undergone potentially curative therapy.
5. Has known active central nervous system (CNS) metastases and/or carcinomatous meningitis. The presence of RCC metastases to other sites is permitted.
6. Has an active autoimmune disease or a documented history of autoimmune disease. Subjects with vitiligo or resolved childhood asthma/atopy are an exception to this rule. Subjects that require intermittent use of bronchodilators will not be excluded from the study.
7. Has a history of (non-infectious) pneumonitis that required treatment with steroids or current pneumonitis.
8. Has an active infection requiring systemic therapy.

9. Is receiving anticoagulant therapy or has received anticoagulant therapy within 10 days prior to screening. Certain platelet aggregation inhibitors are permitted (see Section 5.5.1 below)
10. Has severe cardiovascular disease, i.e. arrhythmias, requiring chronic treatment, congestive heart failure (NYHA Class III or IV) or symptomatic ischemic heart disease.
11. Has hepatic decompensation (Child-Pugh score > 6 [class B and C]).
12. Has uncontrolled thyroid dysfunction. Subjects with hypothyroidism stable on thyroid hormone replacement will not be excluded from the study.
13. Has uncontrolled diabetes mellitus.
14. Has a history or current evidence of any condition, therapy, or laboratory abnormality that might confound the results of the trial, interfere with the subject's participation for the full duration of the trial, or is not in the best interest of the subject to participate, in the opinion of the treating investigator.

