5.5.1 Acceptable Concomitant Medications

All concomitant medication will be recorded on the case report form (CRF) including all prescription, over-the-counter (OTC), herbal supplements, and IV medications and fluids. If changes occur during the trial period, documentation of drug dosage, frequency, route, and date may also be included on the CRF.

All concomitant medications received within 28 days before screening and 30 days after the last dose of trial treatment should be recorded. Concomitant medications administered after 30 days after the last dose of trial treatment should be recorded for SAEs and ECIs as defined in Section 7.2.

Paracetamol/acetaminophen may be used for minor ailments without prior consultation with the investigator or the Sponsor Clinical Director.

Subjects receiving therapy with NSAIDS are permitted to continue this medication throughout the study, as clinically indicated. Subjects receiving other platelet aggregation inhibitors (e.g. Clopidogrel) may continue such medications, provided they are held for at least 5 days prior to pretreatment tumor biopsy and prior to surgical RCC resection, and are not restarted until at least the day following the procedure.

Medications or vaccinations specifically prohibited in the exclusion criteria are not allowed during the ongoing trial. If there is a clinical indication for any medication or vaccination specifically prohibited during the trial, discontinuation from trial therapy or vaccination may be required. The investigator should discuss any questions regarding this with the Sponsor Clinical Director. The final decision on any supportive therapy or vaccination rests with the investigator and/or the subject's primary physician. However, the decision to continue the subject on trial therapy or vaccination schedule requires the mutual agreement of the investigator, the Sponsor and the subject.

Prohibited Concomitant Medications

Subjects are prohibited from receiving the following therapies during the Screening and Treatment Phases of this trial:

- Anti-cancer systemic chemotherapy or biological therapy, other than the study prescribed administration of MK-3475
- Immunotherapy not specified in this protocol
- Chemotherapy not specified in this protocol
- Investigational agents other than MK-3475
- Radiation therapy

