Note: Radiation therapy to a symptomatic lesion or to the brain may be considered on a case-by-case basis after consultation with the Sponsor. Such a radiated lesion should not be a RECIST 1.1 target lesion.

- Live vaccines within 30 days prior to screening and while participating in the trial. Examples of live vaccines include, but are not limited to, the following: measles, mumps, rubella, chicken pox, yellow fever, rabies, BCG, and typhoid (oral) vaccine. Seasonal influenza vaccines for injection are generally killed virus vaccines and are allowed; however intranasal influenza vaccines (e.g. Flu-Mist®) are live attenuated vaccines, and are not allowed.
- Systemic glucocorticoids, for any purpose other than to modulate AEs of suspected immunologic etiology or on the day of surgical RCC resection to modulate perioperative nausea.

Note: If systemic glucocorticoids are administered to a subject receiving MK-3475 during the neoadjuvant phase of the trial to modulate an AE of suspected immunologic etiology, the guidance in Section 5.2.1.2.1.1 should be followed with regard to continued MK-3475 administration.

- Anticoagulants, other than those administered by subcutaneous injection for deep vein thrombosis (DVT) prophylaxis in the perioperative and postoperative period. Prohibited anticoagulants include, but are not limited to heparin (iv), enoxaparin, and warfarin. Note: platelet aggregation inhibitors are permitted with certain restrictions (See Section 5.5.1).

Subjects who, in the assessment by the investigator, require the use of any of the aforementioned treatments for clinical management should be removed from the trial. Subjects may receive other medications that the investigator deems to be medically necessary.

Upon completion of the first visit in the follow-up phase of the trial (See Section 6- Trial Flow Chart), there are no prohibited therapies.

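### Surgery-day research blood has no stated order relative to a permitted steroid, so exploratory baseline-to-surgery blood comparisons can include a steroid effect

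*Combined protocol and SAP*

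**What the plan says.** **Steroid rules.** Exclusion criterion 2 (section 5.1.3) bars anyone who "has received systemic steroid therapy or any other form of immunosuppressive therapy within 4 weeks prior to screening". The list of prohibited medications under section 5.5.1 opens with "Subjects are prohibited from receiving the following therapies during the Screening and Treatment Phases of this trial". It includes systemic glucocorticoids, with two exceptions: adverse events of suspected immunologic cause, "or on the day of surgical RCC resection to modulate perioperative nausea".

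**Sampling.** Section 4.2.3.3 sets the schedule: "Blood will be collected at the time of biopsy (baseline), at the time of surgical tumor resection, and one month postoperatively". For baseline, footnote t of flow chart 6.1 says "Blood and urine samples should be collected on the day of the pretreatment core biopsy". If an earlier diagnostic biopsy is used instead, the samples must still precede the first dose. For surgery, footnote q of 6.1 says "Blood for study related analyses may be collected at any time prior to surgery on the day of surgery" and continues "Ideally these blood samples will be collected via the iv cannula placed in preparation for surgery". Earlier venipuncture that day is allowed at the care team's discretion. Footnote q of 6.3 and footnote n of 6.2 (controls) repeat this.

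**Use.** In 6.1 the footnote q draw supplies PBMC phenotyping, PBMC cryopreservation, plasma, serum, RNA and DNA. Section 4.2.3.3 assigns before/after differences to the drug. Its sentence begins "By comparing profiles in tumor tissues and whole blood collected before and after neoadjuvant MK-3475, changes in gene expression induced during MK-3475 treatment" and says these changes will be identified and used to study how the drug works. Section 8.2.4 relates baseline values and changes in serum and plasma markers to immune infiltration, as exploratory analyses.

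**The concern.** The two samples in the comparison are taken under different steroid rules. At baseline a systemic steroid is ruled out. On the day of surgery one is allowed, and the blood may be drawn before or after it. A patient whose blood is drawn after the steroid contributes a change made up of two effects, and nothing in the planned analysis separates them.

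The documents themselves treat corticosteroids as immune-active. Exclusion criterion 2 groups them with immunosuppressive therapy, and Tables 3 and 6 use them to manage immune-related adverse events. The readouts at risk are immune readouts. This is also the only biomarker blood draw between the first dose and surgery, because the research blood at the dosing visits is serum for PK/PD only. What is at stake is the interpretation of exploratory blood biomarkers in a trial that section 4.2.1.3 says was set up to obtain such specimens.

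**Working it through.** The plan gives no figure to reproduce. The check sets the passages side by side and then asks what can be quantified.

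**1. Is baseline steroid-free?** Yes, by design. Steroids in the 4 weeks before screening exclude the patient, and the prohibition covers screening. The baseline draw precedes the first dose, so the exception for drug-related immune events has no practical role there.

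**2. Can a steroid precede the surgery-day draw without a deviation?** Yes. The exception covers the whole day of resection, the draw may be at any time that day before surgery, and no section orders one relative to the other.

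**3. Could the order be recovered later?** Not reliably. Concomitant medication is reviewed at the resection visit in all three flow charts, so steroid use can be found. But section 5.5.1 says only that the date of a medication may be recorded and does not mention clock time. A same-day steroid and a same-day draw cannot be put in order from a date.

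**4. Does the analysis allow for it?** The readable text of section 8.2.4 has no steroid covariate, exclusion or sensitivity analysis.

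**5. Does another sample replace it?** The postoperative sample (30 to 42 days, section 7.1.5.5) is clear of the surgery-day dose but follows removal of the tumour. Controls have the same steroid allowance but no baseline research blood (6.2), so they have no within-patient change to compare.

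**6. What can be quantified?** Let *p* be the share of treated patients whose surgery-day blood follows a steroid, and *s* the steroid effect on a marker. Take *s* as constant, and steroid timing as unrelated to the drug effect; both are assumptions.

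- Mean observed change = drug effect + *p* × *s*
- Added between-patient variance = *p*(1 − *p*) × *s*²

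The documents give neither *p* nor *s*. At *p* = 0 there is no problem. At *p* = 0.5 the mean shifts by 0.5*s* and the added variance is at its largest, 0.25*s*². At *p* = 1 the mean shifts by the full *s*, the added variance is zero, and excluding post-steroid samples would leave none. Recording times alone is therefore not enough; the order of the draw has to be set in advance.

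**7. How many patients?** From sections 8.2.6 and 8.2.7, the treated number is 12 or 15 at the second interim analysis, 18 or 24 at the third, and 24 or 33 at the end. The range is 12 to 33, so affected treated samples number between 0 and 33.

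**8. Would amending footnote n reach the controls?** Not as 6.2 is labelled. Its surgery-day research-blood rows carry footnote m, which concerns pregnancy testing. Footnote n is attached to coagulation, CBC, chemistry and HLA typing. This looks like a labelling slip, but it must be corrected for a new rule to apply.

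**The case against.** The best case for the plan is that the sequence is allowed but not shown to happen. The exception names the day, not the hour, and a steroid given during or after surgery cannot affect a pre-surgical sample. Blood taken as the cannula is placed would precede any drug given through it. No document states what a single perioperative dose does to any of these markers. The readable analyses are exploratory, and many compare patients with one another; there, steroid timing unrelated to response would mostly add scatter. Steroid use that day can be identified from the medication review, which permits a yes/no sensitivity analysis. Footnote q deliberately leaves timing to the care team.

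Most of this stands, and it limits the point to a cheap improvement. It does not remove it. Section 4.2.3.3 plans a before/after comparison in whole blood and attributes the result to the drug, and there a shift is bias as well as scatter. A yes/no flag would discard samples drawn before the steroid along with those drawn after it. The protocol also accepts the principle for tissue: section 4.2.1.4 wants intraoperative cores taken before the renal artery is clamped, so that changes unrelated to treatment do not enter the comparison.

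Three stronger readings are tempting and not supported:

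- **That the protocol itself declares steroids a confounder.** Criterion 2 gives no reason for the exclusion.
- **That the primary pharmacodynamic endpoint is affected.** Section 8.2.2 defines it on intratumoral lymphocytes, and these footnotes govern blood only.
- **That a count of compromised samples can be given.** Assumed shares of 10% to 50% would give 0.10 × 12 = 1.2 to 0.50 × 33 = 16.5 patients, but nothing in the documents anchors those shares.

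**Conclusion.** The plan permits a steroid-free baseline to be compared with a post-steroid surgery-day sample and the difference to be read as an effect of MK-3475. The affected comparisons are the within-patient changes in PBMC phenotype, whole-blood gene expression and plasma or serum markers. As far as the unredacted text shows, these are exploratory; parts of the secondary and tertiary methods are redacted, so wider use cannot be checked.

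The size of any bias cannot be stated. The share of samples affected lies between 0% and 100% of 12 to 33 treated patients, and the steroid effect is not given. The conclusion rests on two things: the documents set no order between steroid and draw, and a systemic glucocorticoid can move immune markers in blood. The second is inferred from how the protocol uses these drugs, not from a figure in it. This is a low-cost improvement, not an error that threatens the trial's main conclusions.

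**What to change.** 1. In footnote q of 6.1 and 6.3 and footnote n of 6.2, state that surgery-day research blood is drawn before any perioperative glucocorticoid, where one is given before surgery. A sample that misses this is still collected and flagged.
2. In 6.2, change the label on the surgery-day research-blood rows from footnote m to footnote n, so that the rule reaches controls.
3. Record the clock time of the draw and of any glucocorticoid given that day. Also record the date of any systemic steroid given for an immune-related adverse event between baseline and surgery, since that second permitted exposure affects the same comparison.
4. In section 8.2.4, prespecify a sensitivity analysis of the blood-marker comparisons that excludes samples drawn after a steroid.

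The cost is one clause per footnote, one label correction, two time fields, and slightly less freedom for the care team in timing the draw. Footnote q already allows venipuncture earlier that day, so the order is workable. Whether a steroid is given is a clinical matter and is left unchanged.
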